13.2.1 Primary Objective

The primary endpoint will be the ORR, defined by CR or PR as measured by RECIST v1.1.

For patients with disease that progressed after at least one platinum-based treatment regimen, the ORR for atezolizumab monotherapy is 14.8%.

The Cochran Mantel Haenszel test will be conducted to compare ORR in the experimental arm (atezolizumab + CYT107) to the ORR in the control arm (atezolizumab monotherapy). A one-sided significance level of 0.10 will be considered for the test.

13.3 Sample Size/Accrual Rate

During the Safety Run-In phase, 6 patients will be assigned to the experimental arm (atezolizumab + CYT107) with staggered enrollment (refer to [Section 5](#) for details). The AEs will be assessed by the Toxicity Evaluation Committee. If, at any time, 2 or more patients experience a protocol-defined DLT (refer to [Section 5.2](#)), further enrollment into the trial will be suspended.

If the treatment combination of the experimental arm demonstrates an acceptable safety profile in the Safety Run-In (1 or fewer patient experiences a protocol-defined DLT), randomized enrollment into the trial will begin.

A total of 54 patients will be enrolled in this study; 6 patients in the Safety Run-In and 48 patients in the randomized portion of the study. The expected accrual is 4 patients per month total at approximately 8 CITN sites. A study with 48 randomly assigned patients (1:1 randomization) will meet the following statistical parameters: $H_{\text{null}} = 14.8\%$; $H_{\text{alt}} = 45\%$; one-sided alpha of 0.10; power 88%.

The interim futility analysis will be conducted when 24 randomized patients have their first disease assessment and survival information. The futility analysis is based on an O'Brien-Fleming boundary, and the futility boundary will be considered to be crossed when the difference of ORR in the experimental arm – ORR in the control arm is less than -0.0063. Under the null hypothesis, the probability of crossing the futility boundary is 48.2%.

Safety Population: All patients who receive at least 1 dose of the investigational regimen will be considered evaluable for safety and included in the overall safety analysis. For the Safety Run-in phase, in the absence of a DLT, patients must complete the full 28-day DLT window period to be considered evaluable for DLTs. Patients who discontinue from the study before the completion of the full 28-day DLT window for reasons other than the occurrence of a DLT (e.g., withdrawal of consent, rapid tumor progression, death due to rapid tumor progression, AE that does not meet DLT criteria) will not be considered evaluable for DLTs and will be replaced.

Efficacy Population: The efficacy analysis will be conducted on all randomized patients, based upon the intent-to-treat population.

PLANNED ENROLLMENT REPORT

Racial Categories	Ethnic Categories		Totals
	Not Hispanic or Latino	Hispanic or Latino	

	Female	Male	Female	Male	
American Indian/ Alaska Native	1	2			3
Asian	1	4		1	6
Native Hawaiian or Other Pacific Islander	1	1		1	3
Black or African American	2	8	1	3	14
White	3	17	2	6	28
More Than One Race					
Total	8	32	3	11	54

PHS 398 / PHS 2590 (Rev. 08/12 Approved Through 8/31/2015)

OMB No. 0925-0001/0002

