13.4 Stratification Factors

Patients will be randomly assigned to either the control arm (Atezolizumab monotherapy) or experimental arm (Atezolizumab + CYT107) of the trial. The randomization will not be stratified.

The PD-L1 level is considered an important predictive variable. Thus, a stratified analysis by PD-L1 level is considered for analysis as a secondary objective.

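### Section 13.3 states 88% power and a 48.2% futility probability that the named test and the nominal 24:24 and 12:12 allocations do not deliver (minor)

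*Combined protocol and SAP*

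**What the plan says.** Section 13.3 fixes the design: "A study with 48 randomly assigned patients (1:1 randomization) will meet the following statistical parameters", namely 14.8% under the null, 45% under the alternative, and "one-sided alpha of 0.10; power 88" per cent.

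On the interim look it says: "The interim futility analysis will be conducted when 24 randomized patients have their first disease assessment and survival information". The boundary is crossed when the objective response rate (ORR) in the experimental arm minus "ORR in the control arm is less than -0.0063". It then adds: "Under the null hypothesis, the probability of crossing the futility boundary is 48.2" per cent.

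Section 13.2.1 names the analysis: "The Cochran Mantel Haenszel test will be conducted to compare ORR in the experimental arm" with that in the control arm, and "A one-sided significance level of 0.10 will be considered for the test". Section 13.4 adds: "The randomization will not be stratified".

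The text does not give the formula behind either figure, the per-arm split assumed at the look, whether the stop is binding in the power figure, or whether the CMH statistic is continuity-corrected. The opening of Section 13 says that no separate SAP will be issued, so 13.3 is where these details would have to stand.

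**The concern.** These two figures describe how the trial behaves: how often it detects the target effect, and how often it stops early when the combination adds nothing. A reader will take them as properties of the test and rule described beside them.

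Two features suggest that they may not be. First, the usual formulas for two proportions differ by a couple of points at this sample size, and a continuity correction costs several more, so a power figure means little until the test variant is known. Second, with 12 patients per arm the ORR difference moves in steps of 1/12 = 0.083. A cut-off of -0.0063 lies between two attainable values, and a smooth normal curve can misstate the chance of falling below it.

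At stake is the accuracy of the stated operating characteristics, not the validity of the trial.

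**Working it through.** **Inputs.** From 13.3: 14.8% versus 45%, one-sided alpha 0.10, 48 patients 1:1 (nominally 24:24), look at 24 patients (nominally 12:12), cut-off -0.0063. From 13.2.1: CMH test. From 13.4: no stratification, so a single 2x2 table.

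**1. Reproducing 48.2%.** Normal approximation at 12:12, both rates 14.8%:
- SE = sqrt(2 x 0.148 x 0.852 / 12) = 0.1450
- Phi(-0.0063 / 0.1450) = 48.27%

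This matches the stated figure to within rounding, so it is not an arithmetic slip.

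**2. Exact crossing probability.** Let E ~ Bin(nE, 0.148) and C ~ Bin(nC, 0.148), with nE + nC = 24. Sum the joint probabilities where E/nE - C/nC < -0.0063. At 12:12 the rule reduces to E < C, and a tie does not cross:
- P(tie) = 23.2%
- P(E < C) = (1 - 0.2325) / 2 = 38.4%

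| Split (experimental:control) | Exact null crossing |
|---|---|
| 9:15 | 51.0% |
| 10:14 | 50.3% |
| 11:13 | 44.9% |
| 12:12 | 38.4% |
| 13:11 | 52.9% |
| 14:10 | 47.6% |
| 15:9 | 46.4% |

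Weighted by Bin(24, 0.5), the simple-randomization average is 46.5%. With 45% in the experimental arm, crossing at 12:12 has probability 2.7%.

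**3. Trying to reproduce 88%.** At 24 per arm, the difference is 0.45 - 0.148 = 0.302 and the critical value is 1.2816.
- Unpooled: SE = sqrt((0.148 x 0.852 + 0.45 x 0.55) / 24) = 0.1248; power = Phi(0.302 / 0.1248 - 1.2816) = 87.3%.
- Pooled null variance: mean rate 0.299; null SE = sqrt(2 x 0.299 x 0.701 / 24) = 0.1322; power = Phi((0.302 - 1.2816 x 0.1322) / 0.1248) = 85.6%.
- Arcsine: 85.9%.
- Critical value from the 14.8% null variance: 91.4%.
- Unpooled with the futility look included: 86.0%, or 86.6% with a critical value adjusted for a binding stop.

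None gives 88%; the unpooled formula is closest.

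**4. Exact power of the named test.** Full enumeration of the two binomials at 24:24, CMH with hypergeometric variance, rejecting when z >= 1.2816:

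| CMH variant | No stop | Binding stop at 12:12 | Type I error (no stop; stop) |
|---|---|---|---|
| Uncorrected | 85.6% | 85.1% | 10.2%; 10.1% |
| Continuity-corrected | 78.1% | 77.8% | 5.0%; 5.0% |

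**5. Locating the cause of the power gap.** Pooled normal 85.6% against exact uncorrected CMH 85.6%; unpooled normal 87.3% against exact unpooled Z 87.4%. For each statistic the approximation is accurate, so the difference lies between statistics and not between approximate and exact.

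**6. Sensitivity.**
- Final splits from 20:28 to 28:20, uncorrected CMH: 84.5% to 88.5% without the stop, and 84.1% to 87.9% with a 12:12 look. The highest value is at 22:26.
- Averages under simple randomization: 85.7% without the stop; about 84.6% with a binding stop and both splits random.
- If the null response rate at the first assessment were 5% to 10% (an assumption; the documents give no such figure), 12:12 crossing would be 29.1% to 35.9%.

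**The case against.** **The 38.4% is the least favourable split.** This stands. The text does not fix 12:12, which occurs only 16.1% of the time under simple randomization. The neighbouring splits give 44.9% and 52.9%, and the average is 48.2 - 46.5 = 1.7 points below the stated value. A reader might infer that an ineffective combination generally escapes the stop 10 points more often than claimed. That holds only at 12:12; three of the seven splits listed exceed 48.2%.

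**Normal approximations are common in sample-size paragraphs.** This also stands for the futility figure. A reader might infer that 48.2% is an error, but step 1 reproduces it. What is missing is a label and the exact value.

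**88% is within a point of the unpooled formula.** True, but the unpooled statistic is not the test named in 13.2.1. A reader might also infer that 88% is a large-sample figure that fails in small samples. Step 5 rules out that explanation, and because no formula tried gives 88%, its origin should not be asserted.

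**Quoting 85.6% assumes no continuity correction.** Correct: the plan is silent. The choice is worth 85.6 - 78.1 = 7.5 points, more than the gap between 88% and 85.6%. It is the sponsor's to make.

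**Nothing in the conduct of the trial changes.** Agreed; this limits the weight of the point.

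**Conclusion.** The point holds as a minor one. At 24:24 the primary test falls short of the stated 88% by 2.4 points uncorrected (2.9 with a binding 12:12 stop) and by 9.9 points continuity-corrected (10.2 with the stop). The cause is the choice of test or variance. The stated 48.2% is right as a normal approximation, but the exact probability depends on the split: 9.8 points lower at 12:12, and between 3.3 points lower and 4.7 points higher at the other splits from 9:15 to 15:9.

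The power figures assume rates of 14.8% and 45% and 24 per arm; the stop figures also assume a 12:12 look. The futility figures assume that 14.8% already applies in both arms at the first assessment.

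A reader might go further and infer that the trial is underpowered or the futility rule defective. The documents do not support that. The cut-off is unambiguous, uncorrected type I error at 24:24 stays at 10.1% to 10.2%, and a 12:12 stop costs about half a point of power.

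**What to change.** Keep the 24-patient trigger, the -0.0063 cut-off, the 48 patients and the CMH test. Then:

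1. In 13.2.1, have the sponsor state whether the CMH statistic is continuity-corrected.
2. In 13.3, restate the power to match, for 24 per arm: 85.6% uncorrected (85.1% with a binding 12:12 stop), or 78.1% corrected (77.8%). State whether the futility stop is binding.
3. In 13.3, restate the futility probability along these lines: with a 14.8% response rate in both arms, the probability of crossing is 48.2% by normal approximation; by exact calculation it is 38% at 12:12, where equal responder counts do not cross, and about 45% to 53% at uneven splits from 9:15 to 15:9. Add that this assumes 14.8% already applies at the first assessment.

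The cost is one reworded paragraph in 13.3 and a clause in 13.2.1, with a lower stated power. No patients, scans or analyses are added. If the sponsor chooses the corrected test, about 78% becomes the figure on which to judge whether 48 patients suffice.

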13.4 Stratification Factors

Patients will be randomly assigned to either the control arm (Atezolizumab monotherapy) or experimental arm (Atezolizumab + CYT107) of the trial. The randomization will not be stratified.

The PD-L1 level is considered an important predictive variable. Thus, a stratified analysis by PD-L1 level is considered for analysis as a secondary objective.

13.5 Analysis of Secondary Endpoints

13.5.1 Secondary Objectives

Statistical analyses will be conducted for the following secondary objectives:

- The CBR, PFS, DOR, as measured by RECIST v1.1 and irRC, and OS.
- The CBR, PFS, DOR, and OS in patients stratified by PD-L1 expression levels in the tumor microenvironment, as assayed by Genentech.

The CBR is defined as the percentage of patients with advanced or metastatic cancer who have achieved CR, PR, and SD to a therapeutic intervention in clinical trials of anticancer agents. A two-sided test for a difference in proportions will be conducted to compare the CBR in the experimental arm to the CBR in the control arm. A two-sided significance level of 0.05 will be considered for the test.

The PFS, DOR, and OS will be summarized using Kaplan-Meier estimates. Long-rank tests will be conducted for OS and PFS to compare between the 2 arms. A one-sided significance level of 0.10 will be considered.

13.5.2 Exploratory Endpoints

Statistical analyses will be conducted to determine the immune correlates of the clinical activity of the investigational treatment combination.

The endpoints will include the evaluation of the effect of the investigation treatment combination on the immune-bias of the tumor microenvironment, based upon baseline and post-baseline tumor biopsy comparisons of:

- Number, distribution, and phenotype of tumor-infiltrating cells
- PD-L1 expression
- Expression of Interferon γ (IFN γ) and associated proinflammatory gene expression in the tumor microenvironment

Analyses may be also performed to explore the effect of the investigational treatment combination on the number and phenotype of tumor-specific T cells in the peripheral blood, investigate for evidence that the investigational treatment combination increases the exposure of bladder cancer-specific antigens (e.g., Cancer/Testis Antigens or neoantigens), and investigate changes in tumor microenvironment that correlate with response or provide information on potential actionable causes for lack of clinical benefit.

The effect of CYT107 on the infiltrating T cells will be assessed using the paired baseline and post-baseline results of the patients. The patient's baseline result will serve as the control for the comparison. Log-transformed values will be considered for the comparison of the number of infiltrating T cells.

It was established that the CYT107 dose regimen can double the number of peripheral blood T cells. There had been no prior information on the effect of CYT107 on infiltrating T cells. Assuming the CYT107 dose regimen also similarly doubles the number of infiltrating T cells, standard error of the effect size in the log scale (i.e. $\log(\text{post-baseline}) - \log(\text{baseline})$) being 1, and a two-sided alpha of 0.10, a sample size of 13 paired samples will have 80% power to detect any difference between baseline and post-baseline.

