5.1 Agent Administration

Reported adverse events and potential risks are described in [Section 7](#). Appropriate dose modifications are described in [Section 6](#). No investigational or commercial agents or therapies other than those described below may be administered with the intent to treat the patient's malignancy.

Regimen Description					
EXPERIMENTAL ARM					
Agent	Premedications; Precautions	Dose	Route	Schedule	Cycle Length
Atezolizumab	antihistamines or antipyretics/ analgesics ¹	1200 mg	IV	Day 8 of Cycle 1 (28-day cycle) and Day 1 of Cycle 2+ (21-day cycles)	Cycle 1: 28 days Cycle 2+: 21 days
IL-7 (CYT107)²	None	10 mcg/kg	IM	Days 1, 8, 15 and 22 of Cycle 1 only	
CONTROL ARM					
Atezolizumab	antihistamines or antipyretics/ analgesics ¹	1200 mg	IV	Day 1 of each cycle	21 days

Note: ¹Premedication *not* permitted for the first dose on either arm; ²Calculate the required dose amount (10 mcg/kg) based on patient's baseline weight. The dose amount should be recalculated if the patient's weight changes by more than 10% from the baseline weight measurement.

5.1.1 *Atezolizumab*

All patients enrolled into this study will receive atezolizumab. Atezolizumab will be administered on Day 1 of each 21-day cycle in the control arm. Atezolizumab will be administered on Day 8 of Cycle 1 (28-day cycle) and on Day 1 of each subsequent cycle (21-day cycle) on the experimental arm. Atezolizumab may be administered up to 2 days before or after the scheduled administration date of each cycle due to administrative reasons.

Administration of atezolizumab will be performed in a setting with emergency medical facilities and staff who are trained to monitor for and respond to medical emergencies.

Atezolizumab will be administered following the CYT107 injection on Day 8 of Cycle 1 for patients enrolled in the Safety Run-in Phase and experimental arm.

For anaphylaxis precautions, see the management guidelines below. Atezolizumab infusions will be administered per the instructions outlined in the Table below.

First Infusion	Subsequent Infusions

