5.1.2 Recombinant Human IL-7 (CYT107)

Patients enrolled in the Safety Run-in phase and patients randomly assigned to the experimental arm of the trial will receive recombinant human IL-7 (CYT107). The patients will receive 10 mcg/kg of IL-7 (CYT107) IM on days 1, 8, 15 and 22 of Cycle 1 only. The CYT107 dose must be administered before atezolizumab on Day 8 of Cycle 1.

For patient with a Body Mass Index (BMI) >30, an adjusted body weight will be used to calculate the final dose the patient will receive. Please refer to [Appendix D](#) for details on the adjusted body weight calculation.

Patients receiving CYT107 will have their vital signs (heart rate, respiratory rate, blood pressure, and temperature) determined within 60 minutes before the first CYT107 injection on day 1, and 2 hours (\pm 15 minutes) after the injection.

On day 8, vital signs will be monitored as described above ([Section 5.1.1](#)) following the guidelines for the first atezolizumab infusion.

On days 15 and 22, vital signs will be determined within 60 minutes before and within 30 minutes after the injection.

Patients will be informed about the possibility of the development of an allergic reaction to CYT107 (hives, bronchospasm, rash, etc.) and instructed to contact their study physician if they develop such symptoms.

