5.1.3 Other Procedures: Biopsy (core needle, punch or excisional)

The rationale for the biopsy/tissue collection is to investigate changes in the tumor microenvironment that may correlate with response or provide information on potential actionable causes for lack of benefit.

A pre-treatment biopsy/tissue collection will be obtained before the first dose of study treatment (atezolizumab or CYT107) assuming this can be carried out safely.

Note: If an archival tumor sample (at least $0.5 \times 0.5 \times 0.5$ cm) obtained within 2 years from screening visit is available, the pre-treatment biopsy is not required.

A post-treatment tumor biopsy/tissue collection will be obtained if deemed relatively safe and technically feasible (core biopsy, punch biopsy or excisional biopsy). The tumor biopsy/tissue collection will be obtained prior to dosing on Cycle 4, Day 1 or at the end of treatment visit, whichever occurs first.

The biopsies will be done according to clinical site Standard Operating Procedures (SOPs).

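### Section 13.5.2 attributes the within-patient change in tumour-infiltrating T cells to CYT107, although every patient also receives atezolizumab and no comparison with the control arm is specified

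*Combined protocol and SAP*

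**What the plan says.** Section 13.5.2 states: "The effect of CYT107 on the infiltrating T cells will be assessed using the paired baseline and post-baseline results of the patients". Counts are log-transformed, and each patient's own "baseline result will serve as the control for the comparison". Assuming a doubling, a value of 1 for what it calls the "standard error of the effect size in the log scale", and a two-sided alpha of 0.10, it concludes that "a sample size of 13 paired samples will have 80% power to detect any difference between baseline and post-baseline".

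Other sections fix what the patients receive and when tissue is taken:

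- Section 5.1.1: "All patients enrolled into this study will receive atezolizumab". Dosing starts on Day 8 of Cycle 1 in the experimental arm and on Day 1 in the control arm.
- Section 5.1.2: CYT107 is given "on days 1, 8, 15 and 22 of Cycle 1 only".
- Section 5.1.3: the post-treatment biopsy is taken before Cycle 4 Day 1 dosing or at end of treatment, whichever is first, and only where judged safe and feasible. At baseline, if an archival sample "obtained within 2 years from screening visit is available, the pre-treatment biopsy is not required".
- Section 10: the control-arm calendar carries the same post-treatment biopsy rule.

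No section specifies a between-arm comparison of infiltrating T cells. The comparison with and without CYT107 in Section 2.6.2 concerns circulating cells.

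**The concern.** The effect named is that of CYT107, but the comparator is the same patient before any study treatment. Between the two samples the patient receives CYT107 and atezolizumab, time passes, and the tissue may change from archival to fresh. A paired test cannot divide the change among these sources. Pooling control-arm pairs into the same test would not help, because it would still be a change over time.

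The trial asks whether CYT107 adds to atezolizumab (Section 1). A significant rise, read as Section 13.5.2 words it, could be taken as evidence that CYT107 brings T cells into the tumour when it adds nothing. This is also the only exploratory endpoint with a power calculation, so readers may give it more weight than its design supports.

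**Working it through.** **Schedule** (Sections 5.1.1 to 5.1.3 and 10; nominal days, ignoring visit windows)

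| | Experimental | Control |
|---|---|---|
| Cycle 4 Day 1 | 28 + 21 + 21 + 1 = day 71 | 3 × 21 + 1 = day 64 |
| Earlier atezolizumab doses | days 8, 29, 50 | days 1, 22, 43 |
| Days since first atezolizumab | 71 − 8 = 63 | 64 − 1 = 63 |
| Days since last CYT107 | 71 − 22 = 49 | not given |

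At the scheduled biopsy the arms match on number of atezolizumab doses and time since the first one.

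**The plan's figure.** Inputs from Section 13.5.2: δ = ln 2 = 0.693, SD of paired log differences 1, two-sided alpha 0.10, 80% power.

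- n = ((1.645 + 0.842) × 1 / 0.693)² = 12.87, rounded up to 13.
- Power at 13 = Φ(0.693 × √13 − 1.645) = Φ(0.854) = 80.4%.

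The figure reproduces with natural logs, the normal approximation, and 1 read as a standard deviation. Log base 2 would give 7 pairs and base 10 would give 69. If 1 were literally the standard error of the mean change, n would not enter the calculation. A paired t-test (noncentral t, 12 df) has 76.1% power at 13 pairs and needs 15 (81.8%).

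**The paired test when CYT107 adds nothing.** Assume atezolizumab alone multiplies infiltrating T cells by f. The noncentrality for 13 pairs is ln(f) × √13; an increase is declared in the upper 5% tail.

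| f (assumed) | Noncentrality | Chance of declaring an increase |
|---|---|---|
| 1 | 0 | 5% |
| 1.25 | 0.80 | 18.8% |
| 1.5 | 1.46 | 39.5% |
| 2 | 2.50 | 76.1% |

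**A between-arm test of CYT107.** Section 13.3 randomizes 48 patients 1:1, so at most 24 pairs per arm. Assume CYT107 adds a further doubling and the SD of change is 1 in each arm.

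- *Unadjusted change scores:* noncentrality 0.693 / √(2/n), df 2n − 2.
- *ANCOVA* (log post-treatment count adjusted for log baseline): with equal pre and post variances and correlation r, SD of change 1 implies a variance of 1/(2(1 − r)) at each time. The residual SD is then √((1 + r)/2), with df 2n − 3.

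| Analysis | 13 per arm | 24 per arm | Pairs per arm for 80% |
|---|---|---|---|
| Change scores | 52.9% | 76.4% | 27 |
| ANCOVA, r = 0.3 | 68.5% | 90.1% | 18 |
| ANCOVA, r = 0.5 | 63.1% | 86.1% | 21 |
| ANCOVA, r = 0.7 | 58.5% | 82.1% | 23 |

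Simulation with chance baseline imbalance (4,000 runs) gives ANCOVA power of 67/62/57% at 13 per arm and 89/86/81% at 24, for r = 0.3/0.5/0.7. With no CYT107 effect, r = 0.5 and f = 1.25/1.5/2, ANCOVA declares an increase in 4.9/4.9/5.2% of runs at 13 per arm and 4.5/5.0/5.8% at 24. These null rates assume that the patients with pairs are comparable between arms.

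**The case against.** Section 1.3, the hypotheses in Sections 2.5.2 and 2.5.3 and the opening of Section 13.5.2 all concern the combination. A paired design suits that question, so the fault could be called one loose sentence. That is fair as far as it goes, and a wording change alone would remove the contradiction. But the sentence naming CYT107 introduces the endpoint's test and leads into its power statement, and nothing elsewhere supplies the missing comparison.

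The plan does not forbid an arm comparison either; it is silent. That is right: the gap is one of specification.

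The between-arm contrast has limits, and these stand. Biopsies depend on safety and feasibility, and some will be taken at end of treatment. The pairs are therefore a post-randomization subset whose composition and timing could differ by arm if CYT107 affects progression. The match at 63 days holds only for the scheduled biopsy and counts from first atezolizumab; from first study treatment it is 70 days (71 − 1) against 63. The null rate of about 5% is not assured under such selection. The 19%, 40% and 76% come from assumed fold changes and show sensitivity, not an expected error rate.

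**Conclusion.** The concern holds. As written, the analysis cannot identify an effect of CYT107 on infiltrating T cells; it can describe change on the combination. The arithmetic behind 13 pairs is sound by the normal approximation but answers a different question. The size of the possible misattribution depends on what atezolizumab, time and tissue type do on their own, which the documents do not quantify. A between-arm estimate is feasible but not generously powered: 80% for a doubling needs paired tissue from 18 to 23 of 24 patients per arm (75% to 96%) with ANCOVA at r = 0.3 to 0.7. On unadjusted change scores it needs 27 per arm, more than are randomized. The consequence is confined to an exploratory endpoint.

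**What to change.** 1. Define the CYT107 effect as the between-arm difference in log post-treatment count adjusted for log baseline (ANCOVA), with a 90% confidence interval. Use randomized patients only; Section 13.2 already keeps the six run-in patients out of randomized comparisons.
2. Keep the within-arm change as a descriptive result for the combination.
3. Report by arm the number with paired tissue, whether baseline was archival or fresh, and whether the later biopsy was at Cycle 4 Day 1 or end of treatment. State that the pairs are a post-randomization subset.
4. Call the value of 1 the standard deviation of the paired log differences, and state natural log.
5. Say that 80% with 13 pairs is power for within-patient change by the normal approximation (76% by paired t-test, which needs 15 pairs). Give between-arm power separately, with its assumed correlation.

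Minimum alternative: describe the result as change on the combination and make no claim about CYT107's own contribution.

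The cost is some wording and one extra model, with no new biopsies. Section 13 asks only that changes to exploratory analyses be listed and explained in the clinical study report. The drawback is that, with fewer than about 18 to 23 pairs per arm, the stated power for a CYT107 effect falls below 80%, so the result should be read mainly as an estimate with its interval.

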Paired baseline and post-baseline tumor biopsies will be evaluated using quantitative multicolor immunohistochemistry (IHC) with Perkin-Elmer's Vectra IHC platform. This platform employs spectral deconvolution imaging to separate optical signals from each antibody together with state-of-the-art image analysis capabilities to facilitate robust quantitative slide-based immunophenotyping. Using the Vectra multispectral imaging platform (PerkinElmer), adjacent tumor sections will be stained and imaged with a series of 5-6 antibodies per section simultaneously to investigate the spatial relationship between key immunomodulatory cell types and molecules. The antibodies will include, but are not limited to, the following: pancytokeratin (AE1/AE3), CD8, CD4, PD-1, PD-L1, CD68, CD163, FOXP3, arginase, and pan-MHC class I and class II. Data will be generated in the form of total positive cells, positive cells/mm², percentage positive cells in a population, ratios of cells and molecules of interest (e.g., PD-L1:CD8 or FOXP3+CD4+:CD8). Additionally, tumors may also be assayed by IHC for a variety of other markers including CD80, IFN-gamma CD3, CD5, TIA-1, CD20, CD11b, CD137, CD45RO, CD301CD56 and CD16 (natural killer [NK] and NK T cells), CD79a (B cells), GITR, TIM-3, FOXP3, LAG3. Furthermore, quantitative analysis of tumor-infiltrating lymphocyte (TIL) distribution (*i.e.*, stromal, and interface/invasive margin) will be performed. Anti-PD-L1 immunohistochemical staining will be performed at HistoGeneX (Naperville, IL) with the SP142 clone, in addition to the multispectral IHC (msIHC) to serve as both an independent test and control for the reproducibility of the msIHC assay. The study is intended to evaluate for changes in the immune profile of the tumor microenvironment. If sufficient archival tumor tissue collected before therapy is not

available, a baseline biopsy will be obtained before enrolling in the study as part of this protocol.

IHC studies will be performed under the direction of Dr. [REDACTED] at the Fred Hutchinson Cancer Research Center (Fred Hutch) Experimental Histopathology Laboratory, Seattle, WA, or other agreed upon investigator.

Hypothesis: The combination of atezolizumab with CYT107 will alter the TME (tumor microenvironment) towards a pro inflammatory phenotype.

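### Minor, exploratory endpoint: the 80% power stated for 13 paired biopsies holds only if the SD is treated as known; a paired t-test has 76% and needs 15 pairs, and the T-cell metric is not named

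*Combined protocol and SAP*

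**What the plan says.** Section 13.5.2 says that the effect of CYT107 on infiltrating T cells "will be assessed using the paired baseline and post-baseline results of the patients", each patient serving as his or her own control. On scale it says: "Log-transformed values will be considered for the comparison of the number of infiltrating T cells".

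The power statement has four inputs:
- **Effect:** "Assuming the CYT107 dose regimen also similarly doubles the number of infiltrating T cells".
- **Variability:** the "standard error of the effect size in the log scale" is taken as 1. A parenthesis defines the effect as log post-baseline minus log baseline.
- **Level:** "a two-sided alpha of 0.10".
- **Result:** "a sample size of 13 paired samples will have 80% power to detect any difference between baseline and post-baseline".

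No test and no log base are named. The same paragraph acknowledges that nothing was known beforehand about how CYT107 affects infiltrating T cells.

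Section 2.5.2 lists the forms in which the multispectral IHC data will be available: "total positive cells, positive cells/mm², percentage positive cells in a population", plus ratios. Section 13.5.2 does not say which of these is the analysis variable.

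**The concern.** Three things in one short paragraph do not fit together.

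First, a standard error already includes the sample size, so a standard error of 1 cannot be an input from which a sample size is derived. The quantity needed is the SD of the paired log differences.

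Second, 13 pairs is a small sample. With so few pairs, a formula that treats the SD as known overstates the power of the test that would normally be run.

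Third, the endpoint is worded as a number of cells. Under sections 3.1.8, 5.1.3 and 9.1.2.1 the baseline tissue may be an archival block, slides, or a fresh core, punch or excision, and the later sample a core, punch or excision. If a count were analysed, a change in specimen size could pass for a change in infiltration, or hide one.

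What is at stake is limited. This is the only power statement for the tumour T-cell comparison, and section 13 says that no separate SAP will be issued, so 13.5.2 is the place to get it right. No decision rule depends on it.

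**Working it through.** **Inputs.** Doubling, variability 1, two-sided alpha 0.10, 13 pairs and 80% power, all from 13.5.2. Assumed because the text is silent: natural log, and 1 as the SD of the paired log differences.

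**Step 1: reproduce the plan's figure.** The effect is ln 2 = 0.693. The normal approximation for paired data is

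n = ((z₀.₉₅ + z₀.₈₀) × SD / ln 2)² = ((1.645 + 0.842) × 1 / 0.693)² = 12.87, rounded up to 13.

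At n = 13 the standardised effect is 0.693 × √13 = 2.50, and the power is Φ(2.50 − 1.645) = 80.4%. Both stated figures follow, which identifies the natural log and an SD of 1 as the intended inputs.

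**Step 2: let the SD be estimated.** For a paired t-test, power comes from the noncentral t distribution with n − 1 degrees of freedom and noncentrality 0.693 × √n. At n = 13 the critical value rises from 1.645 to 1.782.

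| Pairs | Normal approximation, SD known | Paired t-test |
|---|---|---|
| 13 | 80.4% | 76.1% |
| 14 | 82.9% | 79.1% |
| 15 | 85.1% | 81.8% |

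The t-test first passes 80% at 15 pairs. A Wilcoxon signed-rank test on simulated normal data gives about 73% to 74% at 13 pairs. Keeping 1.645 with an estimated SD would not recover the 80% at the stated level: on 12 degrees of freedom the actual two-sided alpha is about 12.6%.

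**Step 3: sensitivity to the assumed SD.** With 13 pairs and a paired t-test:

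| SD of log change | Power |
|---|---|
| 0.80 | 90% |
| 0.95 | 80% |
| 1.00 | 76% |
| 1.25 | 60% |

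**Step 4: count against density.** If cells per mm² did not change at all, the log count would still shift by ln(later area / baseline area). The documents give no analysed section area, so the sizes here are assumptions. The minimum archival size in 5.1.3 has a 5 mm × 5 mm face, or 25 mm². Against later areas of 5, 10 and 15 mm² the shift is ln(5/25) = −1.61, ln(10/25) = −0.92 and ln(15/25) = −0.51, beside a hypothesised effect of +0.69. With the sizes reversed the sign reverses. Density removes this term.

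**Step 5: pairs available.** Section 13.3 randomizes 48 patients 1:1, so 48 / 2 = 24 are in the experimental arm. Each is scheduled for a post-treatment biopsy where safe and feasible. With SD 1 the paired t-test has 88% power at 18 pairs and 95% at 24. The share who will yield a usable pair is not stated.

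**The case against.** The strongest reply is that nothing is arithmetically wrong: a standard formula gives 13 and 80%, the protocol never commits to a t-test, and SD = 1 is a working guess. A gap of 4 points and two pairs is smaller than the uncertainty in that guess, since an SD of 0.95 would restore 80% at 13 pairs. The endpoint is exploratory, and section 13 allows exploratory analyses to be changed later and listed in the study report.

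Most of this stands, and it is why the point is minor. It does not remove the point. With no prior data on the effect, treating the SD as known has no basis, and the usual tests held to a true 10% level fall short of 80% at 13 pairs.

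Several stronger readings are tempting, and the documents do not support them:
- **Power of 18%.** This follows from taking a standard error of 1 literally. The parenthetical definition as a log difference, and the exact match at 13, show that an SD was meant.
- **Power of 27% or 96%.** These are the t-test figures for log10 and log2 with SD 1. The match at 13 points to the natural log.
- **A raw count will be analysed.** Section 13.5.2 never says raw, and 2.5.2 provides cells/mm². The gap is that no metric is chosen.
- **Biopsies stop at 13 pairs.** No section sets such a stop.

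**Conclusion.** The 80% claim is correct only under a normal approximation with a known SD of 1 on the natural-log scale. With the SD estimated, 13 pairs give 76% and 15 are needed for 80% (82%), a shortfall of about 4 points or two pairs. The label for the variability is wrong, and the claim to detect any difference should be limited to a doubling, because that is the effect the power was computed for.

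The metric is left open where a tissue-dependent count would be an avoidable source of artefact. How large that artefact could be rests entirely on assumed section areas.

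A reader might infer that the mechanism comparison is badly underpowered or that the trial needs more patients. Neither follows: 24 experimental patients are already scheduled for the second biopsy where feasible. All power figures here depend on SD = 1, for which the documents give no data on either the count or the density scale. The primary ORR analysis is untouched.

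**What to change.** Replace the power sentence in 13.5.2 with wording such as: *Assuming a doubling and an SD of 1 for the within-patient change in natural-log T-cell density (positive cells/mm²), a two-sided 0.10 paired t-test has 76% power with 13 pairs and 82% with 15 pairs to detect a doubling.* Name log density, not log number, as the analysis variable in the preceding paragraph, and say that the SD of 1 is a working assumption.

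The cost is about two sentences and a slightly less favourable stated power. The assay already produces density, so no new measurement is needed, and no enrolment is added.
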